## 12.4 ECOG Performance Status

GRADE	ECOG PERFORMANCE STATUS
0	Fully active, able to carry on all pre-disease performance without restriction
1	Restricted in physically strenuous activity but ambulatory and able to carry out work of a light or sedentary nature, eg, light house work, office work
2	Ambulatory and capable of all self-care but unable to carry out any work activities; up and about more than 50% of waking hours
3	Capable of only limited self-care; confined to bed or chair more than 50% of waking hours
4	Completely disabled; cannot carry on any self-care; totally confined to bed or chair
5	Dead

<http://ecog-acrin.org/resources/ecog-performance-status>

## **12.5 Common Terminology Criteria for Adverse Events V4.0 (CTCAE)**

The descriptions and grading scales found in the revised NCI Common Terminology Criteria for Adverse Events (CTCAE) version 4.0 will be utilized for AE reporting. (<http://ctep.cancer.gov/reporting/ctc.html>).

## **12.6 Response Evaluation Criteria in Solid Tumors (RECIST) 1.1 Criteria for Evaluating Response in Solid Tumors**

RECIST version 1.1\* will be used in this study for assessment of tumor response. While either CT or MRI may be utilized, as per RECIST 1.1, CT is the preferred imaging technique in this study.

\* As published in the European Journal of Cancer [46].

**12.7 Dose Modification Table (based on modified Toxicity Profile Interval [33])**

Sample size = 40a; Target probability  $p_T = 30\%$ ;  $\epsilon_1 = \epsilon_2 = 0.05$ .

Any doses with a dose reduction probability falling into the interval  $(p_T - \epsilon_1, p_T + \epsilon_2)$  will be considered an acceptable dose level.

		Number of Patients																		
		1	2	3	4	5	6	7	8	9	10	11	12	13	14	15	16	17	18	
Number of Toxicity	0	E	E	E	E	E	E	E	E	E	E	E	E	E	E	E	E	E	E	
	1	D	S	S	S	S	E	E	E	E	E	E	E	E	E	E	E	E	E	
	2		D	D	S	S	S	S	S	S	S	E	E	E	E	E	E	E	E	
	3			D	D	D	S	S	S	S	S	S	S	S	S	S	E	E	E	
	4				D	D	D	D	D	S	S	S	S	S	S	S	S	S	S	
	5					D	D	D	D	D	D	S	S	S	S	S	S	S	S	
	6						D	D	D	D	D	D	D	S	S	S	S	S	S	
	7							D	D	D	D	D	D	D	D	S	S	S	S	
	8								D	D	D	D	D	D	D	D	D	D	D	S
	9									D	D	D	D	D	D	D	D	D	D	D
	10										D	D	D	D	D	D	D	D	D	D
	11											D	D	D	D	D	D	D	D	D
	12												D	D	D	D	D	D	D	D
	13													D	D	D	D	D	D	D
	14														D	D	D	D	D	D
	15															D	D	D	D	D
	16																D	D	D	D
	17																	D	D	D
	18																		D	D

**LEGEND**

**E**: Stay at same dose or escalate to the next higher dose (escalation will only apply if the initial dose has been lowered, as doses higher than 800 mg/m^2 for 5-FU and 80 mg/m^2 for cisplatin will not be studied); **S**: Stay at the same dose; **D**: De-escalate to a lower dose;

a. Subjects enrolled at Asian sites and non-Asian sites will be assessed separately. If the dose level for one subgroup has been lowered while the other remains at the higher starting dose, then consideration may be made to increase the dose back to the starting dose based on tolerability in the individual subgroup and the overall population across subgroups.

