### **5.2.1.2 Dose Modification**

If appropriate, the Investigator may attribute each toxicity event to cisplatin, 5-FU (or capecitabine) or pembrolizumab alone in the combination arms and use a stepwise dose reduction according to [Table 4](#) to [Table 8](#). For individual subjects requiring a dose modification, treatment for each new cycle may be delayed if the scheduled off-drug periods are not adequate to allow for recovery to Grade  $\leq 1$  or the baseline status of the subject.

Pembrolizumab/placebo dose reductions are not permitted. Pembrolizumab/placebo treatment may be interrupted or discontinued due to toxicity. If a dose reduction for toxicity occurs with any agent, the dose may not be re-escalated. Subjects can have a maximum of 2 dose modifications (if applicable) to each of the components of study therapy throughout the course of the study for toxicities. If a subject experiences several toxicities and there are conflicting recommendations, please follow the most conservative dose adjustment recommended (dose reduction appropriate to the most severe toxicity). Subjects who require a 3rd dose modification to any particular component will have that agent discontinued.

Reduction of one chemotherapy agent and not the other agent is appropriate if, in the opinion of the Investigator, the toxicity is clearly related to one of the treatments. If, in the opinion of the Investigator, the toxicity is related to the combination of both chemotherapy agents, both drugs should be reduced according to recommended dose modifications. If the toxicity is related to the combination of three agents, chemotherapy should be reduced, interrupted or discontinued; pembrolizumab/placebo should be interrupted or discontinued according to the recommended dose modifications. If a decision is made to discontinue combination chemotherapy due to treatment related AE(s), the subject can be unblinded after discussion with sponsor to identify study treatment. Subjects receiving pembrolizumab therapy may have both the cisplatin and 5-FU or capecitabine discontinued and continue on pembrolizumab alone, while subjects on combination with placebo (arm 3) may discontinue from study treatment.

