## **8.7 INTERIM ANALYSES**

### **8.7.1 Safety Interim Analysis**

An interim safety analysis will take place after 10 subjects in each treatment arm have completed 1 cycle of therapy. Interim periodic safety monitoring will include review of AE data by the eDMC as specified in the DMC charter.

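### Appendix 12.7 keeps a group-level chemotherapy dose rule, run by region, that no section invokes and that conflicts with the dose rules in the body of the protocol

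*Combined protocol and SAP*

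**What the plan says.** **Appendix 12.7.** The appendix is listed in the table of contents and printed in full. It gives a grid of stay-or-escalate (E), stay (S) and de-escalate (D) decisions for 1 to 18 patients, headed "Sample size = 40", with a target probability of 30% and a tolerance of 0.05 on each side. The text defines an acceptable level by the phrase "Any doses with a dose reduction probability falling into the interval", while the grid counts toxicities; neither event is defined. The footnote sets the unit of decision: "Subjects enrolled at Asian sites and non-Asian sites will be assessed separately". The legend covers 5-FU and cisplatin only and allows upward moves: "escalation will only apply if the initial dose has been lowered". It adds that, where one subgroup has been lowered and the other has not, "consideration may be made to increase the dose back to the starting dose based on tolerability in the individual subgroup" and in the overall population.

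**The body.** Section 1.0, Table 1, Table 3 and Sections 5.2.3.3 and 5.2.3.4 give one starting dose of cisplatin and of 5-FU, with no regional level. Section 5.2.1.2 sends the investigator to Tables 4 to 8 for reductions in individual subjects: "Subjects can have a maximum of 2 dose modifications (if applicable) to each of the components of study therapy". It also states: "If a dose reduction for toxicity occurs with any agent, the dose may not be re-escalated". The only early look in the statistical section is in 8.7.1: "An interim safety analysis will take place after 10 subjects in each treatment arm have completed 1 cycle of therapy". No dose decision is attached to it. None of these sections mentions Appendix 12.7.

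**The concern.** The protocol holds two dose rules for the chemotherapy backbone, and they cannot both be followed as written. One acts on the individual and moves only downwards. The other acts on a regional subgroup and can move back up.

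The appendix also lacks what is needed to run it. It does not say which arms are counted, whether Arms 2 and 3 move together, who decides, when, or what applies to subjects on capecitabine, which is a permitted backbone and a stratification factor.

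This matters to a statistician because H1 to H3 and H7 ask what pembrolizumab adds to chemotherapy. A reader of those results needs to know that the backbone was common to Arms 2 and 3, and the text as it stands does not settle that.

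**Working it through.** **1. Is the appendix a complete rule or stray text?** Inputs from Appendix 12.7: target 0.30 and tolerance 0.05, so the acceptable interval is 0.25 to 0.35. The prior is not given; I assume Beta(1,1). With x toxicities in n patients the posterior is Beta(1 + x, 1 + n − x), with distribution function F. The modified toxicity probability interval rule takes the largest of

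- E: F(0.25) / 0.25
- S: [F(0.35) − F(0.25)] / 0.10
- D: [1 − F(0.35)] / 0.65

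For 4 of 10: F(0.25) = 0.1146 and F(0.35) = 0.3317, giving E = 0.46, S = 2.17, D = 1.03. The decision is S, as printed.

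For 5 of 10: F(0.25) = 0.0343 and F(0.35) = 0.1487, giving E = 0.14, S = 1.14, D = 1.31. The decision is D, as printed.

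Over the whole grid, 188 of the 189 entries compared agree. The exception (8 of 18) lies in a row that, as extracted, has 12 entries for 11 columns, so I do not count it as an error. The appendix is a working decision rule.

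**2. The passages side by side.**

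- *Starting dose.* Tables 1 and 3 and Section 5.2.3 give one level for all regions. Appendix 12.7 allows Asian and non-Asian sites to be at different levels.
- *Unit of decision.* Section 5.2.1.2 and Tables 4 to 8 act on the subject. Appendix 12.7 acts on a subgroup.
- *Direction.* Section 5.2.1.2 bars re-escalation of a reduced dose. Appendix 12.7 permits it at subgroup level and does not restrict it to new entrants, so the two collide for any subject already reduced.
- *Occasion.* Section 8.7.1 counts by arm and decides no dose. Appendix 12.7 counts by region and names no occasion.

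**3. What it could do to the treatment comparisons.** The documents do not say which of two readings applies.

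- *Both chemotherapy arms together, within region.* Asia is its own level of the randomisation factor (Section 5.4), and the log-rank and Cox analyses are stratified by region (Section 8.6.1). The Asian/non-Asian split therefore falls along stratum boundaries. Within each stratum Arms 2 and 3 share a backbone, and concurrent randomisation covers changes over time. H1 to H3 remain comparable; only regions differ.
- *By arm.* Arms 2 and 3 could then carry different backbones, and H1 to H3 and H7 would no longer isolate pembrolizumab.

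**4. Would the rule be inert if it were run?** This is an illustration only: the documents give no dose-reduction rate and no group size. Take two groups of 10 with the same true rate p. The chance d of an instruction to de-escalate is P(X ≥ 5) for a binomial(10, p), and the chance that exactly one group gets it is 2d(1 − d).

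- p = 0.20: d = 0.0328; 2 × 0.0328 × 0.9672 = 0.063
- p = 0.30: d = 0.1503; 2 × 0.1503 × 0.8497 = 0.255
- p = 0.40: d = 0.3669; 2 × 0.3669 × 0.6331 = 0.465

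With 18 per group the same calculation gives about 1%, 11% and 39%. If the rule were in force, regional doses could diverge by chance alone.

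**5. Power.** With power = Φ(√(events/4) × |ln HR| − z):

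- H2 (415 events, HR 0.70, one-sided 1.25%): Φ(3.633 − 2.241) = 91.8%
- H1 (430 events, HR 0.65, one-sided 0.10%): Φ(4.466 − 3.090) = 91.6%

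Both match the stated 91% or so, and neither uses anything from Appendix 12.7.

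**The case against.** The strongest reply is that 12.7 is leftover text. Section 5.2.1.2 invokes only Tables 4 to 8. The appendix heading cites reference 33, a review of palliative chemotherapy, although the interval-method paper is reference 1. A grid that starts at one patient, with a size of 40, is an early-enrolment device. The original protocol dates from May 2015 and this one from January 2019, against an assumed 19-month enrolment, so enrolment was probably over. This is a fair inference, but the documents do not confirm it. It argues for removing the appendix rather than leaving it.

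A second reply is that the bar on re-escalation is written for individual subjects and the appendix for a subgroup level. This also stands in part. The direct clash is confined to subjects already reduced, and avoiding it needs a restriction that the text does not contain.

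A third is that the arms counted, the decision-maker and the timing may be in the DMC charter, which is not available here. That is possible, but a charter would not remove the conflict between the protocol's own sections.

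Three stronger inferences are tempting, and the documents do not support them.

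- *Pembrolizumab's effect is confounded with chemotherapy dose, or the blind is broken.* Nothing in 12.7 points to counting Arm 2 alone. An arm-specific count by sites or sponsor would breach the blinding in Sections 2.1 and 5.2.4.
- *Sites and the DMC are working to two rules.* One rule is invoked; the other is an orphaned table.
- *The 57% Grade 3-4 neutropenia reported for cisplatin/5-FU in Section 4.2.2.1 makes de-escalation likely.* That figure is not a dose-reduction rate. Tables 7 and 8 call for no reduction at Grade 3 neutropenia, and no Grade 4 rate is given.

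Nor was the backbone ever wholly uniform: the fluoropyrimidine is chosen by local guideline, and cisplatin may stop at six cycles under country guidelines.

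**Conclusion.** The inconsistency is real and in the current text. A group-level, region-by-region dose rule stands in the protocol uninvoked, and it conflicts with the single starting dose, with the subject-level reductions and, for subjects already reduced, with the bar on re-escalation. It names no arm and omits capecitabine.

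The consequence for inference is conditional. H1 to H3 are protected if Arms 2 and 3 would move together within region. They are exposed only under an arm-specific reading that the text neither states nor excludes. Nothing shows that the rule was ever applied.

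The divergence probabilities in the working rest on assumed rates and group sizes and show only that the rule would have practical effect if run. The match to the printed grid rests on an assumed flat prior. No power, alpha or sample-size figure changes. The point deserves correction because it is cheap to settle and bears on how the primary contrasts are read.

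**What to change.** Reconcile Appendix 12.7 with Section 5.2.1.2, Tables 1, 3 and 4 to 8, Section 5.2.3 and Section 8.7.1. If 12.7 is not in force, remove it. Have the sponsor state whether any group-level change of cisplatin or 5-FU dose was made, so that readers know whether the backbone was common to Arms 2 and 3. Which dose rule is right is for the sponsor to settle.

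The cost is a protocol clarification and one sentence of disclosure, with no new data, visits or subjects.

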## 12.8 List of Abbreviations

Abbreviation/Term	Definition
1L	First Line
2L	Second Line
5-FU	5-fluorouracil
AE	Adverse Event
ADA	Anti-Drug Antibodies
ALT	Alanine Aminotransferase
ANC	Absolute Neutrophil Count
AP	Alkaline Phosphatase
ASaT	All Subjects as Treated
aPTT	Activated Partial Thromboplastin Time
ASCO	American Society of Clinical Oncology
AST	Aspartate Aminotransferase
AUC	Area Under the Curve
BICR	Blinded Independent Central Review
BID	Twice a Day
β-HCG	Beta Human Chorionic Gonadotropin
BSA	Body Surface Area
CBC	Complete Blood Count
CI	Confidence Interval
CNS	Central Nervous System
CPS	Combined Positive Score
CR	Complete Response
CrCl	Calculated Creatinine Clearance
CRF	Case Report Form
CSR	Clinical Study Report
CT	Computed Tomography
CTCAE	Common Toxicity Criteria for Adverse Events
CTLA-4	Cytotoxic T-Lymphocyte-Associated Antigen-4
CTU	Computed Tomography Urography
DCR	Disease Control Rate
DMC	Data Monitoring Committee
DNA	Deoxyribonucleic acid
DOR	Duration of Response
DR	Drug Related
ECI	Events of Clinical Interest
ECG	Electrocardiogram
ECOG	Eastern Cooperative Oncology Group
eDMC	external Data Monitoring Committee
EOC	Executive Oversight Committee
EORTC	European Organization for Research and Treatment of Cancer
ePRO	Electronic Patient Reported Outcomes
ERC	Ethics Review Committee
FA	Final Analysis
FBR	Future Biomedical Research
FDA	Food and Drug Administration
FDAAA	Food and Drug Administration Amendments Act
FDAMA	Food and Drug Administration Modernization Act
FFPE	Formalin-Fixed, Paraffin-Embedded
FNA	Fine Needle Aspirate

Abbreviation/Term	Definition
FP	Cisplatin + 5-fluoruracil
GCP	Good Clinical Practice
GEJ	Gastroesophageal Junction
5-FU	5-fluoruracil
GFR	Glomerular Filtration Rate
HBsAg	Hepatitis B surface Antigen
HCV	Hepatitis C Virus
HER2/neu	Human Epidermal Growth Factor Receptor 2
HIV	Human Immunodeficiency Virus
HNSCC	Head and Neck Squamous Cell Carcinoma
HPV	Human Papillomavirus
HRQoL	Health Related Quality of Life
IA	Interim Analysis
IB	Investigator's Brochure
ICF	Informed Consent Form
ICH	International Conference on Harmonization
IEC	Independent Ethics Committee
IHC	Immunohistochemistry
INR	International Normalized Ratio
irAEs	Immune-related Adverse Events
irRECIST	Modification of RECIST 1.1
IRB	Institutional Review Board
ITIM	Immunoreceptor Tyrosine-based Inhibition Motif
ITSM	Immunoreceptor Tyrosine-based Switch Motif
ITT	Intention To Treat
IV	Intravenous
IVRS	Interactive Voice Response System
IWRS	Integrated Web Response System
Kg	Kilogram
KN	KEYNOTE
LDH	Lactate Dehydrogenase
mAb	Monoclonal Antibody
mcL	Microliters
MEL	Melanoma
Mg	Milligram
Mg/kg	Milligram per Kilogram
mL	milliliter
MRI	Magnetic Resonance Imaging
MSD	Merck Sharp & Dohme Corp., a subsidiary of Merck & Co., Inc.
MTD	Maximum Tolerated Dose
NA or N/A	Not Applicable
NCI	National Cancer Institute
NSAID	Non-Steroidal Anti-inflammatory Drug
NSCLC	Non-Small Cell Lung Cancer
ORR	Overall Response Rate
OS	Overall Survival
OTC	Over-the-counter
PD	Progressive Disease
PD-1	Programmed Death-1
PD-L1	Programmed Death-Ligand 1
PFS	Progression Free Survival

Abbreviation/Term	Definition
PGt	Pharmacogenetic
PIN	Personal Identification Number
PK	Pharmacokinetic
PK/PD	Pharmacokinetic/Pharmacodynamic
PO	Oral Administration
PR	Partial Response
PRO	Patient Reported Outcomes
PT	Prothrombin Time
PS	Performance Status
QoL	Quality of Life
R/M	Recurrent or Metastatic
RECIST	Response Evaluation Criteria in Solid Tumors
RNA	Ribonucleic Acid
RR	Response Rate
QoL	Quality of Life
Q2W	Every 2 Weeks
Q3W	Every 3 Weeks
SAC	Scientific Advisory Committee
SAE	Serious Adverse Events
SAP	Statistical Analysis Plan
SD	Stable disease
SFU	Survival Follow-Up
SGOT	Serum Glutamic Oxaloacetic Transaminase
SGPT	Serum Glutamic Pyruvic Transaminase
siDMC	Standing Internal Data Monitoring Committee
SIM	Site Imaging Manual
SOC	Standard of Care
SOP	Standard Operating Procedures
T1DM	Type 1 Diabetes Mellitus
TIL	Tumor Infiltrating Lymphocytes
TSH	Thyroid Stimulating Hormone
ULN	Upper Limit of Normal
WBC	White Blood Cell

